2. PURPOSE/HYPOTHESIS

We propose to test an innovative MRI breast cancer screening protocol in women with mammographically dense breasts as well as other women with moderately increased cancer risk. MRI, combined with other methods of risk assessment, has potential to significantly improve sensitivity to cancer in dense breasts and detect cancer in all cases at a much earlier stage, with far fewer interval cancers than mammography [8, 9].

Previous tests of MRI sensitivity show that this screening could significantly increase the likelihood of detecting invasive cancers resulting in decreased mortality from breast cancer [1]. Effective MRI-screening would have an exceptional impact in the region surrounding the UC Medical Center, where rates of breast cancer are unusually high, and where the prevalence of aggressive breast cancer is also very high. If MRI screening can identify breast cancers, particularly the most aggressive subtype of breast cancer, several years earlier than conventional methods, this would have tremendous benefits for patients.

We propose to develop fast, accurate, quantitative, and inexpensive MRI screening methods that can easily be implemented in routine clinical practice. This research will build on innovative work from this team that has significantly advanced breast MRI, including dynamic contrast enhanced MRI of the breasts. This is an opportunity for the University to have a significant impact, initially in our immediate neighborhood, and eventually nationally and internationally. This is an area where the University should lead because of the devastating effect of breast cancer in south Chicago.

The specific purpose of the study is as follows:

1. Develop an efficient, quantitative MRI-screening protocol, less than 15 minutes in duration. Evaluate signal-to-noise ratio and reproducibility in 10 volunteers with dense breasts.

2. Scan approximately 50 women with mammographic or sonographic findings that require biopsy using the short MRI protocol (15 minutes), to establish reasonable cutoffs for MRI parameters derived from the short protocol, that are likely to identify benign and malignant lesions with high sensitivity.
3. In partnership with the Cancer Risk Clinic and the Breast Center, we will identify and recruit 150 women with dense breasts and/or intermediate risk of breast cancer who will also undergo the short MRI protocol.

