4. Perform a reader study to evaluate false positive rate, based on the cutoffs established in women with biopsy proven benign and malignant lesions.
5. Perform quantitative analysis to determine standard DCEMRI protocols including Ktrans (the rate constant for contrast media uptake; [2-4]). In addition, we will test novel parameters that can be extracted from ultrafast datasets; initial time of enhancement in parenchyma and suspicious lesions, new approaches to calculating Ktrans and the arterial input function based on early enhancement, and number and size of arteries feeding suspicious lesions and rate of enhancement of those blood vessels. These markers can be accurately calculated from ultrafast imaging but cannot be accurately measured with conventional methods. Determine the rate of false positives based on the cutoffs for each of these parameters determined from the study of women with confirmed breast cancer ('2' above).
6. Suspicious lesions will be defined by the clinical interpretation of the breast MRI images performed by the attending breast radiologist. Based on the radiologist determination that the MRI findings are suspicious (these findings include masses, non-mass enhancement and foci), suspicious lesions will be assigned a Bi-Rads code specifying whether additional work up or biopsy is necessary. These are BiRads codes 0, 4 and 5. False positive diagnosis should be minimized as all attending physicians reading breast MRI at this institution are fellowship trained in breast imaging.

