Thirty women with biopsy-confirmed breast cancer and between sixty and seventy controls (women with dense breasts and/or moderate breast cancer risk, frequency-matched by parity, age, and menopausal status; control group also includes some women with biopsy-proven benign lesions) will be scanned using the short MRI protocol. Receiver Operating Characteristic (ROC) curves and statistics will be constructed for several MRI parameters of interest: Ktrans, initial time of enhancement in parenchyma and suspicious lesions, new approaches to calculating Ktrans and the arterial input function based on early enhancement, and number and size of arteries feeding suspicious lesions and rate of enhancement of those blood vessels. The primary endpoints of this study are Ktrans and 'initial time of enhancement'. Optimal diagnostic thresholds will be determined for each parameter, where the optimal threshold for a given parameter is defined as the parameter value which has highest sum of specificity and sensitivity over all possible thresholds with specificity > 80%. We will also test whether the area under the curve (AUC) for each parameter exceeds 60%. 95% confidence intervals will be constructed for the AUC for each curve and the sensitivity and specificity of each optimal threshold. For our two primary endpoints (Ktrans and initial time of enhancement), our sample of 200 subjects (30 cases + 170 controls) is large enough to detect AUCs of 74% (i.e., a difference of 14%) at the 5% significance level.

Thresholds determined in this pilot study will later be validated in a larger cohort – this is the subject of an RO1 proposal to be submitted soon. In the future cohort, we will construct covariate-adjusted ROC curves that will be used to calculate thresholds, specificities, and sensitivities for patients with different breast cancer risk factors (Gail scores, family history, etc.).

We will also produce ROC curves for each reader in the 'reader study' to obtain a preliminary estimate of how standard evaluation of abbreviated MRI datasets compare with the quantitative analysis described above. However, this is an exploratory aim of the study and the study is not powered to evaluate the statistical confidence of these measurements.

6. PROCEDURES TO WHICH HUMANS WILL BE SUBJECTED:

Patients with lesions detected on mammography or ultrasound:

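### The statistical section and the study purposes disagree on how many controls there are, which women set the parameter cutoffs, and by which criterion

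*Combined protocol and SAP*

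**What the plan says.** **Section 5, Statistical Power.** The section opens with 30 cancers and "between sixty and seventy controls", drawn from women with dense breasts or moderate risk, and adds that the "control group also includes some women with biopsy-proven benign lesions". ROC curves are planned for several MRI parameters, with Ktrans and initial time of enhancement as primary endpoints. Each parameter's AUC is tested against 60%, and its cutoff is the value with the "highest sum of specificity and sensitivity over all possible thresholds with specificity > 80" percent. The power sentence then uses a different count: "our sample of 200 subjects (30 cases + 170 controls) is large enough to detect AUCs of 74" percent, at the 5% level. Neither power nor sidedness is given. The section adds: "Thresholds determined in this pilot study will later be validated in a larger cohort".

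**Section 5, Enrollment.** About 50 women with suspicious findings are expected to yield 30 cancers and 20 benign lesions. A further 150 women form the screening group.

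**Section 2.** Item 2 uses the roughly 50 biopsy women to set cutoffs "that are likely to identify benign and malignant lesions with high sensitivity". Item 4, the reader study, evaluates a false positive rate "based on the cutoffs established in women with biopsy proven benign and malignant lesions". Item 5, for the quantitative parameters, finds the rate of false positives from the "cutoffs for each of these parameters determined from the study of women with confirmed breast cancer", and refers back to item 2.

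**The concern.** The two sections describe different procedures for the same primary-endpoint cutoffs.

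- **Count.** Section 5 gives 60-70 controls and 170 controls.
- **Source.** Section 5 defines only one control group, so its natural reading is that the AUC test and the cutoff rule both apply to screening women and benign biopsies together. Section 2 takes the cutoffs from biopsied women only.
- **Criterion.** Section 2 wants high sensitivity and gives no figure. Section 5 sets a specificity floor and no sensitivity target.

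Two analysts who each followed the plan faithfully could report different cutoffs for Ktrans and initial time of enhancement, and so different false positive rates. Those cutoffs are meant to go forward to a larger cohort. Also, most of the pooled controls are screening women, so a satisfactory pooled AUC or specificity need not say much about separating cancer from benign lesions. No separate AUC or specificity for that contrast is planned.

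**Working it through.** **1. Control count.** 150 screening + 20 expected benign = 170. This matches the power sentence. No other count in the documents matches 60-70.

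**2. Reproducing the 74%.** Inputs: null AUC 0.60, alternative 0.74, 30 cases, 170 controls, 5% level (Section 5). Sidedness and power are not stated, so both sidedness options are tried and 80% power is assumed. The Hanley-McNeil variance is

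Var(A) = [A(1-A) + (n1-1)(A/(2-A) - A²) + (n0-1)(2A²/(1+A) - A²)] / (n1·n0).

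- At A = 0.60: (0.24 + 29×0.0686 + 169×0.0900)/5100 = 0.00342, SE 0.0585.
- At A = 0.74: (0.1924 + 29×0.0397 + 169×0.0818)/5100 = 0.00297, SE 0.0545.
- Power, one-sided: Φ[(0.14 - 1.645×0.0585)/0.0545] = Φ(0.80) = 78.9%.
- Power, two-sided: Φ[(0.14 - 1.96×0.0585)/0.0545] = Φ(0.47) = 67.9%.

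The Obuchowski binormal variance gives 81.1% and 71.2%. At an assumed 80% power the detectable AUC is 0.738-0.742 one-sided and 0.755-0.760 two-sided. The stated 74% therefore fits 30 v 170 on a one-sided 5% basis at about 80% power.

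**3. Effect of the count conflict alone.** With 60-70 controls, on the same one-sided basis, the detectable AUC is 0.750-0.755 and power at 0.74 is 72-75%. The change is small because the 30 cases dominate the variance.

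**4. What the specificity floor implies if the pool sets the cutoff.** Specificity above 80% of 170 requires more than 136 negatives, so at most 170 - 137 = 33 false positives.

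- Observed pooled false positive rate: at most 33/170 = 19.4%.
- Observed rate in screening women: up to 33/150 = 22%, if no benign lesion is positive.
- Benign lesions: all 20 could be positive and the rule still met, provided at most 33 - 20 = 13 of the 150 screening women are positive.

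**5. Pooled AUC.** It is the weighted mean of the two component AUCs, with weight 150/170 = 88% on screening women. A pooled 0.74 is compatible with 0.50 against benign lesions and 0.772 against screening women: (20×0.50 + 150×0.772)/170 = 0.74.

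**6. Illustration of source and criterion.** The documents give no component AUCs, so these are assumed. The markers are unit-variance normal, with a mean difference of √2·Φ⁻¹(AUC) between cancers and each control type. There are 30 cancers, 20 benign and 150 screening women, with 4,000 simulated trials per setting. Every screening woman is assumed to contribute a value comparable with a lesion's. The figures are true values at the chosen cutoff, averaged over trials.

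*Source: the Section 5 rule applied to the pool or to the biopsy group alone.*

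| AUC v benign / v screening | Benign specificity, pooled cutoff | Benign specificity, biopsy-group cutoff |
|---|---|---|
| 0.74 / 0.74 | 84% | 84% |
| 0.70 / 0.75 | 79% | 84% |
| 0.70 / 0.80 | about 73% | 84% |

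*Criterion, at 0.74/0.74.* High sensitivity is taken as 27 of 30 cancers positive, an assumed 90%.

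| Cutoff | Sensitivity | Screening false positives |
|---|---|---|
| Biopsy group, 27/30 positive | 87% | about 60% |
| Section 5 rule, pooled | 46% | 16% |

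The source matters only when the two control types differ. The criterion matters even when they do not.

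**The case against.** The strongest reply is that this is a pilot whose cutoffs will be validated later. On that view Section 2 states a loose aim, and Section 5 can be read as its operational definition. A maximum-sum rule with a specificity floor can also yield a sensitive cutoff. All of that is fair, but it does not settle which women set the cutoff, and Section 5 guarantees no level of sensitivity.

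Several further objections stand and limit the point.

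- A reader might infer that the rule also constrains the reader-study rate in item 4. The documents do not support this: Section 5 defines the rule for MRI parameters, readers score on a 1-10 scale, and the reader study is declared exploratory and unpowered.
- A reader might infer that the false positive rate in screening women is capped below 20%. It is not. The limit applies to the observed pooled rate, arises only if screening women help set the cutoff, and leaves room for 22% in the screening group.
- The illustration needs a marker value from every screening woman. The documents do not say what a woman without a lesion contributes. If only women with a measurable lesion enter a lesion-based curve, the 88% weight and the simulated figures do not apply to that parameter.
- The 60% v 16% contrast depends on the assumed 90% target. At an AUC of 0.74, any cutoff that sensitive produces many false positives.
- Setting cutoffs in biopsied women, as Section 2 does, already uses the cancer-benign contrast. What is missing is a planned report of its AUC and specificity.

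**Conclusion.** The point holds as a conflict within the plan, and it should be fixed. Control count, cutoff source and cutoff criterion each differ between passages that no other text reconciles. The last two bear directly on the primary-endpoint cutoffs.

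The consequence that needs no modelling is that, if the pool sets the cutoff, the observed pooled false positive rate is below 20% by construction and is not the separate application of biopsy-group cutoffs described in item 5. The size of any difference in cutoffs rests on assumptions. Under the normal model it is nil for source at equal component AUCs, about 11 points of benign specificity (84% v 73%) at 0.70/0.80, and about 44 points of screening false positives (60% v 16%) for criterion at 0.74/0.74.

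Two stronger conclusions might be drawn and are not supported. The 74% is not wrong: it reproduces for 30 v 170, one-sided, at about 80% power, and falls to 68-71% power only if a two-sided test was intended. Nor are mixed controls a mistake: they suit the question of false positives in screening women, so the pooled result is incomplete rather than invalid. The count conflict taken alone is minor.

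**What to change.** 1. Use one control count throughout Section 5, and state the sidedness and power behind the 74%.
2. Reconcile Section 2 (items 2 and 5) with Section 5 on which women set the parameter cutoffs and by which criterion; if high sensitivity is intended, give the figure. Report the false positive rate in screening women separately from the data that set the cutoff. If screening women do help set it, label their rate as in-sample.
3. Keep the pooled analysis. Add, descriptively and with 95% confidence intervals, AUC, sensitivity and specificity for cancer v biopsy-group benign lesions and for cancer v screening women. Show benign lesions that were selected on MRI within the screening group (biopsied, or assumed benign under Ground truth assignment, item c) separately, not merged with the 20. State what value a woman without a lesion contributes to each curve.

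The cost is wording plus a stratified table on data already collected, with no added women or scans. The downside is imprecision in the benign contrast: a benign specificity of 17/20 has an exact 95% interval of 62-97%. For that reason it should be presented as estimation, and it needs no power statement of its own.

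### Sections 2 and 5 derive the cutoffs from different groups, and section 5 reports each optimised threshold's accuracy on the data that chose it, uncorrected (minor)

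*Combined protocol and SAP*

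**What the plan says.** **Section 2 (Purpose/Hypothesis).** Item 2: "Scan approximately 50 women with mammographic or sonographic findings that require biopsy using the short MRI protocol (15 minutes), to establish reasonable cutoffs", with the aim that they identify lesions with high sensitivity. Item 4: "Perform a reader study to evaluate false positive rate, based on the cutoffs established in women with biopsy proven benign and malignant lesions". Item 5, on the quantitative parameters: "Determine the rate of false positives based on the cutoffs for each of these parameters determined from the study of women with confirmed breast cancer", referring back to item 2. No numerical rule for choosing a cutoff is given here.

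**Section 5 (Study Design, Statistical Power).** ROC curves compare 30 cancers with controls who are mainly dense-breast or moderate-risk women plus some with benign biopsies. The controls number "between sixty and seventy controls" in one sentence, but in another "our sample of 200 subjects (30 cases + 170 controls) is large enough". The optimal threshold is the value with the "highest sum of specificity and sensitivity over all possible thresholds with specificity > 80" per cent. Then: "95% confidence intervals will be constructed for the AUC for each curve and the sensitivity and specificity of each optimal threshold". No split sample, resampling or optimism correction is described. On later work: "Thresholds determined in this pilot study will later be validated in a larger cohort". The plan adds that the future cohort will be used to calculate thresholds, specificities and sensitivities again.

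**The concern.** There are two linked problems.

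First, the false-positive rate is a stated purpose of the study. Section 2 ties it to cutoffs from the biopsy group. Section 5 reports specificity, its complement, at thresholds found in a different sample by a rule that section 2 does not mention. The two rates mean different things. One is measured in women who had no part in setting the cutoff; the other is limited by the selection rule. A reader of the results could not tell which was reported, and the choice could be made after the data are seen.

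Second, a threshold chosen to maximise sensitivity plus specificity looks better in the sample that chose it than in new women. Section 5 puts 95% intervals on those same-sample figures without saying that they are optimistic.

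**Working it through.** **1. The plan's own figure.** The only figure to reproduce is the detectable AUC of 0.74 against 0.60 with 30 + 170 at the 5% level. With m = 30, n = 170, Q1 = A/(2−A) and Q2 = 2A²/(1+A), the Hanley-McNeil variance is [A(1−A) + (m−1)(Q1−A²) + (n−1)(Q2−A²)]/(mn).

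- At A = 0.60: (0.240 + 1.989 + 15.210)/5100 = 0.00342, SE 0.0585.
- At A = 0.74: (0.192 + 1.151 + 13.83)/5100 = 0.00297, SE 0.0545.
- One-sided 5% power = Φ((0.14 − 1.645 × 0.0585)/0.0545) = Φ(0.80), about 79%.

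So 0.74 reproduces if the test is one-sided with about 80% power; the plan states neither. Threshold selection does not enter this test. The plan gives no sensitivity, specificity or optimism figure to reproduce.

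**2. The cap in section 5's rule.** Specificity must exceed 80%, so the most false positives allowed among all controls are:

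- 170 controls: at least 137 negative, so 33/170 = 19.4%.
- 60 controls: 11/60 = 18.3%.
- 70 controls: 13/70 = 18.6%.

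The cap is over all controls. If all 33 false positives were screening women, their own rate would be 33/150 = 22%. A cutoff set only in the biopsy women places no such limit on the 150 screening women.

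**3. Optimism from scoring on the selecting sample.** Assumed model: controls N(0, 1), cancers N(μ, σ²), AUC = Φ(μ/√(1+σ²)). For each simulated trial:

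- apply section 5's rule to get t*;
- apparent sensitivity = (cancers at or above t*)/30, and true sensitivity = 1 − Φ((t*−μ)/σ);
- apparent specificity = (controls below t*)/n, and true specificity = Φ(t*);
- optimism = apparent − true.

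Mean optimism in points, over true AUC 0.60 to 0.90, σ of 1 or 1.5, and cutting at an observed value or midway between values (6,000 trials per setting):

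| Cancers v controls | Sensitivity | Specificity |
|---|---|---|
| 30 v 170 | +4.4 to +5.5 | +0.6 to +1.1 |
| 30 v 65 | +3.8 to +5.3 | +1.5 to +2.5 |
| 30 v 20 (biopsy group, section 5's rule assumed) | +2.7 to +4.5 | +4.3 to +6.2 |

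Example: at AUC 0.74, σ = 1, 170 controls and observed-value cutoffs, apparent sensitivity averages 50.7% against a true 45.9%, a gap of 4.8. Separate runs over AUC 0.60 to 0.85 with equal SDs gave +3.5 to +5.4 in sensitivity for 60 to 170 controls. At 30 v 20 they gave +2.9 to +4.4 in sensitivity and +4.8 to +6.5 in specificity.

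**4. Count parameters.** Section 5 also lists the number of feeding arteries. With assumed Poisson counts, the same rule gave sensitivity optimism of 0.2 to 0.8 points. This depends on the assumed means, and larger counts can take it slightly past 1 point.

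**5. Scale.** One cancer is 1/30 = 3.3 points, so 4 to 5.5 points is between one and two cancers (4/3.3 = 1.2; 5.5/3.3 = 1.7). The sampling SE at 15/30 is √(0.5 × 0.5/30) = 9.1 points, and the exact 95% interval is 31% to 69%. If exact limits are used (the plan names no method), they miss true sensitivity in 3.6% to 6.4% of trials. Nearly all misses have the lower limit above the truth.

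**6. What internal validation does.** Repeated 10-fold cross-validation of the full search (AUC 0.74, midpoint cutoffs):

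| Controls | Sensitivity bias | Specificity bias | Sensitivity RMSE, apparent v validated |
|---|---|---|---|
| 170 | +4.3 to −0.3 | +0.9 to 0.0 | 9.8 v 9.9 |
| 65 | +4.1 to +0.4 | +2.3 to −0.2 | 9.6 v 9.8 |

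Exact limits on out-of-fold specificity counts missed in 8.6% (170) and 7.5% (65) of trials at AUC 0.74, and in 12.0% and 11.3% at AUC 0.60. Ordinary limits on apparent specificity missed in 4.2% to 4.9%.

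**The case against.** The best defence has four parts.

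- **Pilot status.** The plan calls this a pilot, will validate the thresholds in a larger cohort, and will recalculate sensitivity and specificity there. This stands as mitigation for future use. It does not correct or label the figures that this study reports.
- **Two different objects.** Section 2's reasonable, high-sensitivity cutoffs and section 5's optimal thresholds may be separate things, which would make this a gap in wording rather than a contradiction. That is possible, but the plan never says so or says which one governs. Item 4 is the weaker support, since it concerns an exploratory reader study scored from 1 to 10. Item 5 concerns the quantitative parameters directly.
- **Size.** The bias is below sampling error, and validation does not reduce total error. Both are true, and they limit the severity. But the interval displays sampling error, while this bias runs in one direction and is not disclosed.
- **Control count.** The 60-70 against 170 conflict is a separate matter. It is noted here only because it sets the denominator, and it adds no weight to this point.

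A reader might also infer that sensitivity is scored on the selecting cancers whichever section governs. The documents do not support that: from the biopsy-group cutoffs, section 2 plans only a false-positive rate. Sensitivity with intervals appears only in section 5. Nor can a range for the screening false-positive rate under section 2 be derived, because section 2 states no rule for its cutoffs.

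**Conclusion.** The point holds, as a minor one. The cutoff source differs between sections 2 and 5, and it decides whether the false-positive rate is out of sample and uncapped or held below 20% over all controls by construction. Section 5's sensitivity and specificity are same-sample figures with no stated correction.

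Under the binormal assumption, for continuous parameters including Ktrans and initial time of enhancement, the optimism is about 4 to 5.5 points in sensitivity and 1 to 2.5 in specificity with 60 to 170 controls. If section 5's rule were applied to the biopsy group alone, which is an assumption, it would be about 3 to 4.5 and 5 to 6.5 points; the 4.3 in the table arises only at AUC 0.90 with σ = 1.5. For a count parameter, sensitivity optimism is likely below 1 point. These are model results, not figures from the plan.

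It would be too strong to conclude that the intervals are invalid or the AUC test inflated. Two-sided exact coverage stays near 95%, and the AUC test uses no threshold.

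**What to change.** 1. Reconcile sections 2 and 5: for each reported quantity, name one source of cutoffs and one number of controls.
2. Label same-sample sensitivity and specificity as apparent. Beside them give internally validated point estimates that repeat the whole constrained search, for example by repeated 10-fold cross-validation. Do not attach exact limits to out-of-fold counts.
3. If biopsy-group cutoffs give the false-positive rate, lock them before scoring the 150 screening women. If pooled cutoffs are used, note the built-in cap below 20% over all controls and report the rate beside sensitivity.

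**Cost.** Some analysis code and wording; no extra participants or scans. On the runs above, the validated sensitivity is lower than the apparent one by 4.3 + 0.3 = 4.6 points (170 controls) or 4.1 − 0.4 = 3.7 (65). Specificity is lower by about 1 to 2.5 points. The gain is an estimate with little mean bias and honest labelling; RMSE does not improve.
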